## 8. STATISTICAL METHODOLOGY AND STATISTICAL ANALYSES

### 8.1. Statistical METHODS

#### 8.1.1. Analyses for Binary Data

Response rates and mortality rates at each timepoint will be presented with exact 95% confidence intervals for binomial proportion, using the Clopper-Pearson method which employs the F-distribution to obtain percentiles of the binomial distribution (Collett 1991).

#### 8.1.2. Analyses for Time-to-Death Data

The analysis of time-to-death will be summarized graphically using the Kaplan-Meier product limit estimator.

Subjects who do not have the event of interest will be censored at the last available observation, as defined in [Section 6.1.5.4](#). A censoring variable will be used, with a value of 1 denoting that the subject had the event of interest and 0 indicating that the subject is censored. A time variable is also required, defined as  $T = [\max(\text{date of event, latest date in database}) - \text{first treatment date} + 1]$ . Summaries of observed median survival time with upper and lower quartiles will be provided.

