#### 7.4.2.4. Micro Response at the 2-Week and 6-Week Follow-Up Visits

Microbiologic response is defined as follows:

- **Eradication or presumed eradication:** Baseline pathogen not isolated from original site culture(s), or culture data are not available for a subject with successful outcome;
- **Persistence (documented or presumed):** Any baseline *Candida* spp. is present in repeat cultures, or culture data are not available for subject with a clinical outcome of failure;
- **Indeterminate:** Culture data are not available for a subject with a clinical outcome of indeterminate;
- **Relapse (recurrence):** Any baseline *Candida* spp isolated following eradication (documented or presumed); or culture data are not available for a subject with a clinical response of failure after a previous response of success;
- **New Infection:** Subject presenting with clinical failure with the emergence of new *Candida* spp at the original site of infection or at a distant site of infection.

In addition, subjects will be contacted (eg, in person, by telephone, mail, or e-mail) to determine survival status at 2-Week and 6-Week after EOT. If a subject cannot be contacted, survival status may be obtained through a family member, hospital/clinic records or information that is in the public domain.

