3. **Tissue Cultures:** For subjects *with microbiologically confirmed ICC* whose screening cultures were obtained from sterile site samples (other than blood), follow-up cultures from the same anatomical site should be repeated only as clinically indicated, otherwise they are not required. For subjects *without microbiologically confirmed ICC*, cultures will be obtained as clinically indicated at the discretion of the investigator. The results of the cultures should be recorded on the case report form.

Investigators will send specimens (blood or other) to their local certified laboratory for culture (incubation should be a minimum of five days if not positive before then). Each laboratory will follow its usual procedures for identification of the species and susceptibility testing to marketed agents.

Additionally, all *Candida* isolates must be preserved for shipment to the reference laboratory to confirm identification and perform susceptibility testing. This includes the original isolate that the diagnosis for inclusion into the study was made, as well as all subsequently recovered *Candida* isolates from any sterile site. If more than one species of *Candida* is isolated from a single culture, all isolates must be sent to the reference laboratory. The susceptibility testing will be conducted using the current Clinical and Laboratory Standards Institute (CLSI) approved standard method.

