## 6. ENDPOINTS AND COVARIATES

This section defines endpoints and covariates only. Statistical analysis details are found in [Section 8](#).

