#### **6.1.5.4. Time to Death**

For this analysis, time to death will be measured from the first dose of study medication in days. For subjects who died, time to death is defined as:

$$T = \text{date of death} - \text{first treatment date} + 1$$

where date of death will be recorded on the End of Study page and/or Infection Notice of Death page. These observations will be regarded as events for the purposes of time to event analyses.

Subjects who are not known to have died, will be censored at their last known survival date taken as the latest date in the database. Time to death is defined as:

$$T = \text{latest date in the database} - \text{first treatment date} + 1$$

where the latest date is expected to be the date of the End of Study visit.

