All-cause mortality rate at EOIVT	MITT	Descriptive only	Candida species	Death	Secondary Analysis
All-cause mortality rate at EOT	MITT	Descriptive only	Age categories	Death	Secondary Analysis
All-cause mortality rate at EOT	MITT	Descriptive only	Candida species	Death	Secondary Analysis
All-cause mortality rate at Week 2 FU	MITT	Descriptive only	Age categories	Death	Secondary Analysis
All-cause mortality rate at Week 2 FU	MITT	Descriptive only	Candida species	Death	Secondary Analysis
All-cause mortality rate at Week 6 FU	MITT	Descriptive only	Age categories	Death	Secondary Analysis
All-cause mortality rate at Week 6 FU	MITT	Descriptive only	Candida species	Death	Secondary Analysis
Time to death (all cause mortality)	MITT	Kaplan-Meier	Age categories	Censored	Secondary Analysis

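### SAP 8.1.2 sets survival time by the later of event date and last database date, contradicting 6.1.5.4 for children who died; as a lesser point, the mortality table counts unknown status as death without labelling it worst case

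*SAP*

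**What the plan says.** **Survival time.** SAP Section 6 states its own role: "This section defines endpoints and covariates only". Within it, 6.1.5.4 gives two rules. The first begins "For subjects who died, time to death is defined as" and counts from first treatment to the date of death, plus one day. The second censors subjects not known to have died at the latest date in the database, "where the latest date is expected to be the date of the End of Study visit".

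SAP 8.1.2 refers back to 6.1.5.4 for censoring and introduces an event indicator (1 for death, 0 for censored). It then gives one time variable for everybody, the maximum of "date of event, latest date in database", minus first treatment date, plus one. That formula is not conditioned on the indicator. The section also commits to quartiles: "Summaries of observed median survival time with upper and lower quartiles will be provided".

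**Unknown survival status.** SAP 6.1.5.3 defines the mortality rate as the proportion who died, out of those in the study population at the start. Section 7 has a missing-data rule for global response and a pointer for safety endpoints, but nothing for mortality. Sections 8.1.1 and 8.2.2 add none. Only Table 8.2.5 has a rule. Its missing-data entry is death in all eight mortality rows, for example "All-cause mortality rate at Week 6 FU MITT Descriptive only Age categories Death Secondary Analysis". The Kaplan-Meier row of the same table censors.

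**The concern.** One endpoint has two formulas in one SAP. A programmer working from the methods section would override the date of death whenever a later date exists for that child. The error can go only one way, because taking a maximum never shortens survival.

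The protocol suggests how later dates could arise, though it does not show that they do. Under Protocol 7.8.5 cultures have a long turnaround ("incubation should be a minimum of five days if not positive before then"), so a sample taken shortly before death could be finalised after it. Protocol 7.4.2.4 adds follow-up contact: "In addition, subjects will be contacted (eg, in person, by telephone, mail, or e-mail) to determine survival status at 2-Week and 6-Week after EOT". The SAP does not say whether dates of either kind count towards the latest date in the database.

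For the mortality rate, the stake is labelling. A figure that counts children of unknown status as dead is an upper bound, and a reader who sees only the rate and its exact interval could take it for observed mortality.

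**Working it through.** The plan states no figure on this point, so there is none to reproduce. The study is descriptive and no sample size was calculated.

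**1. The two formulas side by side.** Let D be the day of death and L the day of the last dated record, both counted from first treatment as Day 1.

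- 6.1.5.4, child who died: T = D.
- 8.1.2, child who died: T = max(D, L).
- Child not known to have died: both sections give T = L.

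The difference for a death is max(0, L − D). With D = 10:

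| Days from death to last record | T by 6.1.5.4 | T by 8.1.2 |
|---|---|---|
| 0 | 10 | 10 |
| 7 | 10 | 17 |
| 14 | 10 | 24 |
| 42 | 10 | 52 |

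**2. Effect on a planned summary.** Inputs are N = 60 (planned evaluable subjects) and 18 deaths, which is 30%, the paediatric mortality that the protocol background says is approached. The death days are assumed: 3, 5, 7, 9, 11, 13, 15, 18, 21, 24, 29, 34, 39, 44, 49, 54, 59, 64. Half fall by Day 21, the adult anidulafungin median time to death in Protocol 1.3.2. Survivors are censored at Day 100.

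The lower quartile is the first day on which estimated survival is 75% or less. That is the 15th death, since 45/60 = 75%, and it falls on Day 49.

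- A 5-day gap for one child changes the quartile only if that child is the 15th death (Day 49 becomes Day 54). For the other 17 deaths it stays at Day 49.
- A 14-day gap for one child changes it for 3 of the 18: the 13th (to Day 53), the 14th and the 15th (each to Day 54).
- If every death had the gap, the quartile would be Day 54 (5 days) or Day 63 (14 days). No passage supports a gap for every death, so these are outer limits.
- Estimated mortality at the end of the curve stays at 18/60 = 30.0% throughout.
- With 14 deaths (23.3%, close to the adult 22.9%), survival never falls to 75% and the lower quartile is not reached. Only the shape of the curve can change.

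**3. What is not affected.** The visit mortality rates in 6.1.5.3 count subjects who died by each timepoint. They do not use T.

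**4. Unknown status counted as death.** Each living child of unknown status adds 1/N, which is 1.7 points at N = 60 and 5 points in an age stratum of 20. The numbers unknown below are assumptions. Intervals are exact (Clopper-Pearson) 95%, as in SAP 8.1.1.

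| Known deaths / N | Unknown | Observed deaths / N | Missing = death | Kaplan-Meier range |
|---|---|---|---|---|
| 18/60 | 0 | 30.0% (18.8–43.2) | 30.0% (18.8–43.2) | 30.0% |
| 18/60 | 3 | 30.0% (18.8–43.2) | 35.0% (23.1–48.4) | 30.0–31.6% |
| 18/60 | 6 | 30.0% (18.8–43.2) | 40.0% (27.6–53.5) | 30.0–33.3% |
| 4/20 | 2 | 20.0% (5.7–43.7) | 30.0% (11.9–54.3) | 20.0–22.2% |

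The Kaplan-Meier range runs from all unknowns censored after the last death (deaths/N) to all censored before the first: 18/57 = 31.6%, 18/54 = 33.3%, 4/18 = 22.2%.

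**The case against.** **On survival time.** The right rule is already in the SAP, in the section that defines endpoints, and 8.1.2 refers to it. SAP 6.1.5.4 says that the date of death comes from the End of Study page or the notice-of-death page, and it expects the latest date to be the End of Study visit. For a child who died, the two dates may well coincide, and the maximum then changes nothing. The possible routes to a later date are thin. The incubation text is a laboratory instruction, and nothing says that a result date is stored. The survival contact is printed under the endocarditis and osteomyelitis section and matters only where a death is learned of late. All of this stands, and it limits how likely the error is. It does not reconcile the formulas, because 8.1.2 is explicit and unconditional.

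A reader might infer that some survival times will be wrong, or that reported mortality will be too low. The documents support neither: no later-dated record is shown, and the visit proportions do not use T. Nor should the maximum be read as a study-wide date, since 6.1.5.4 ties the latest date to each subject's last known survival.

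**On unknown status.** Counting missing as death is prespecified and conservative, and it parallels missing = failure for global response. SAP 8.2.2 already plans counts of died, censored and alive at each follow-up visit, and a summary of causes of death. The interim outputs include death listings. The protocol asks for every effort to document outcome (6.7) and lets survival status come from family, records or public sources (7.4.2.4), so few children may be unknown. This largely stands and leaves a matter of labelling. A reader might also see an error in the proportion counting as dead a child whom Kaplan-Meier censors. Censoring is normal for that estimator, and the two need not agree.

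**Conclusion.** The contradiction between SAP 8.1.2 and 6.1.5.4 is real and should be removed. Its effect is conditional on a child who died having a later-dated record, and is zero otherwise. Where it occurs, survival is lengthened by the full gap, the curve shifts and a reached quartile may move. In the assumed 18-death example, one 5-day gap moves the lower quartile for only 1 of 18 deaths, by 5 days.

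The unlabelled missing = death rule is a secondary point. The choice is defensible. What is missing is a statement of it where the endpoint is defined, and a label. Its size depends on a number of unknowns that the documents do not give.

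Both are minor corrections to a descriptive secondary endpoint. No hypothesis test or decision rule depends on them, and the primary safety objective is untouched.

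**What to change.** In SAP 8.1.2, replace the single formula with two cases matching 6.1.5.4. When the event indicator is 1, T runs to the date of death. When it is 0, T runs to the last date known alive. Say that a date on which the child was not observed or reported alive, such as a laboratory result date, does not count as that date.

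In SAP 6.1.5.3 or Section 7, state the rule for unknown survival status. If missing = death is kept, label it worst case in Table 8.2.5, and show the observed deaths, the number of unknown status and N beside it at each timepoint. Observed deaths divided by N is the matching lower bound, since it treats every unknown child as alive.

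The cost is one formula, one sentence and some table labels, made before database release. No new data or subjects are needed.

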## 8.2. Statistical Analyses

Efficacy analyses will be performed on the MITT population for all analyses, with additional supportive analyses being performed using the PP populations where stated. Visit windows will be used (see [Appendix 1.1](#)). The observation occurring closest to the planned visit day (non-missing) will be summarized. In the instance that 2 observations are equidistant, the latest observation will be used.

### 8.2.1. Primary Analysis

The primary analysis is to examine safety and tolerability of anidulafungin. The set of subjects for this evaluation will be the Safety population. The following parameters will be summarized: rates of discontinuation, adverse events, visual tests, physical examination, ECG findings (if applicable), and laboratory abnormalities. The analysis methods are described in [Section 8.2.4](#).

### 8.2.2. Secondary Analyses

#### Global Response

For each age category, analysis of global response rate at EOIVT, EOT, 2 weeks FU, and 6 weeks FU will be produced for the MITT analysis set. The summary will include the number of observations and estimated rates overall and for each age category.

This analysis will also be performed for each *Candida* species, combining across the age groups.

In order to investigate the robustness of the results, a sensitivity analysis will be carried out. This analysis will investigate the effect of 'indeterminate' and 'missing' global response on the analysis by excluding these subjects from the analysis of global response.

Analysis of global response success rate only for those subjects who completed study treatment at EOIVT, EOT, 2 week follow-up and 6 week follow-up visits will be produced for the MITT population.

A summary of Global Response, Clinical Response and Microbiological response will be produced for the MITT population. For Clinical Response, this will give a count of the number of subjects in each of the categories 'Cure', 'Improvement', 'Failure', 'Indeterminate', and 'Missing'. For Microbiological response, this will give a count of the number of subjects in each of the categories 'Eradication', 'Presumed Eradication', 'Persistence', 'Indeterminate', and 'Missing'. This will be presented overall, for each age category and for each *Candida* species.

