### **6.9. Discontinuation Criteria for Abnormal Liver Function Tests**

It is important for investigators to monitor carefully for any adverse events, including elevations of liver function tests that could be related to anidulafungin.

Subjects who experience an increase in AST, ALT or total bilirubin that exceeds either one of the two thresholds outlined below, at any time during the study, must be discontinued from treatment with anidulafungin.

- AST and/or ALT >3x the upper limit of normal AND total bilirubin >1.5x the upper limit of normal, and no evidence of biliary obstruction (eg, elevated alkaline phosphatase in the context of gallbladder disease, bile duct disease or malignancy) or other explanation (eg, viral hepatitis, autoimmune hepatitis);
- AST and/or ALT >10x the upper limit of normal, regardless of causality.

Note: These subjects will be discontinued from study treatment but will remain in the study for safety monitoring according to the procedures described in [Section 6.7](#). These subjects are required to return for the 2- and 6-week follow-up visits.

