#### **6.10. Discontinuation Criteria for Persistent Candidemia**

Subjects who were either candidemic at baseline or become candidemic during the course of the study will be considered treatment failures and discontinued from study treatment if candidemia persists for more than 7 days.

Note: These subjects will be discontinued from study treatment but will remain in the study for safety monitoring according to the procedures described in [Section 6.7](#). These subjects are required to return for the 2- and 6-week follow-up visits.

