## 1. AMENDMENTS FROM PREVIOUS VERSION(S)

This SAP is an amendment of version 1.0.

The analysis of the global response endpoint has been clarified. Other minor changes have been made to bring the SAP in agreement with Protocol Amendment 3.

This SAP is an amendment of version 2.0. The changes have been made to bring the SAP in agreement with protocol Amendment 4. The primary changes for Protocol Amendment 4 allow enrolment of subjects with *Candida* endocarditis and *Candida* osteomyelitis.

This SAP is an amendment of version 3.0. The changes have been made to tighten up the definition of the global response endpoint.

This SAP is an amendment of version 4.0. The changes have been made to conduct additional analysis with subjects who completed study treatment.

This SAP is an amendment of version 5.0. This amendment reflects the changes that were made in protocol amendments 8 and 9, which include expansion of enrolment criteria to include infants (aged 1 month - < 2 years) who do not have microbiologically confirmed *Candida* but who are at high risk of candidiasis, analysis of pharmacokinetic parameters of polysorbate 80, and addition of an interim analysis.

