### 5.3. Other Analysis Sets

#### 5.3.1. Per-Protocol Analysis Set

The Per-Protocol (PP) analysis set will consist of the subjects in the MITT population, who in addition:

- Have completed a minimum of 10 days of treatment with IV anidulafungin, unless declared a clinical and/or microbiologic failure;
- Have received total antifungal treatment (IV only, IV+Oral) for a minimum duration of 14 days, unless declared a clinical and/or microbiologic failure;
- Have not received more than 48 hours of systemic antifungal therapy (for treatment of current *Candida* infection) prior to first dose of study drug;
- Must not have a prosthetic device and/or vascular catheter (including central venous catheter or an implantable port) at a suspected site of infection are to be excluded, unless the device is removed at study entry or soon after first dose of study drug;

- Have not taken more than 1 day of protocol prohibited antifungal therapy concomitant with study therapy, unless declared a clinical and or microbiologic failure;
- Have reached the 6 weeks Follow up visit unless the subject died or withdrew consent prior to 6 week follow up;

And also exclude those subjects with protocol violations that could have an impact on the efficacy endpoints (See [Section 5.3.2](#)).

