#### 6.1.1. Global Response at the End of IV Treatment (EOIVT)

##### 6.1.1.1. Global Response Determination at EOIVT

Global response at EOIVT is based on assessment of clinical and microbiological response provided by the investigator at this time point, and will be programmatically determined as follows:

**Success:** A patient will be categorized as having successful response if there is a clinical response of cure or improvement and microbiological eradication or presumed eradication.

**Failure:** A patient will be categorized as having an unsuccessful response if there is a clinical response of failure and/or unsuccessful microbiological response (persistence or new infection at FU or relapse at FU).

**Indeterminate:** A patient will be categorized as indeterminate if there is a clinical response of indeterminate and /or microbiological response of indeterminate and neither clinical response is a failure nor unsuccessful microbiological response (persistence or new infection or relapse).

A global response determination of failure at EOIVT will be carried forward programmatically to all subsequent visits.

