## 7. HANDLING OF MISSING VALUES

For global response, missing values are treated as failures. Sensitivity analyses will also be performed in which subjects with missing values for global response are excluded from the analysis.

For the analysis of safety endpoints, the sponsor data standard rules for imputation will be applied.

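### The completers-only global response rate drops subjects whom the protocol itself declares failures and takes off treatment, so it will tend to exceed the full-MITT rate

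*SAP*

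**What the plan says.** SAP 8.2.2 (Global Response) plans, besides the main MITT analysis, an "Analysis of global response success rate only for those subjects who completed study treatment" at EOIVT, EOT and both follow-up visits. The amendment history in SAP section 1 gives no rationale beyond this: "The changes have been made to conduct additional analysis with subjects who completed study treatment". The SAP does not define completion of study treatment. The analysis has no row in the SAP 8.2.5 summary table and no title in the Appendix 2 interim list, so nothing labels it as sensitivity or supportive.

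Three other provisions bear on it:

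- Protocol 6.10: subjects who are candidemic at baseline or later "will be considered treatment failures and discontinued from study treatment if candidemia persists for more than 7 days". They are not lost to follow-up: "These subjects will be discontinued from study treatment but will remain in the study for safety monitoring".
- SAP 6.1.1.1: "A global response determination of failure at EOIVT will be carried forward programmatically to all subsequent visits". SAP 6.1.2 and 6.1.3 say the same for failures at EOT and at the 2-week visit.
- SAP 5.3.1 sets a minimum treatment duration for the Per-Protocol set, with an exception: "Have completed a minimum of 10 days of treatment with IV anidulafungin, unless declared a clinical and/or microbiologic failure". The completers sentence has no such exception.

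For the main analysis, SAP section 7 states: "For global response, missing values are treated as failures".

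**The concern.** Whether a child completes treatment is settled after baseline and depends partly on how the infection responds. Under protocol 6.10 the dependence is built in: lasting candidemia brings the label of failure and the end of treatment together. A death from Candida infection during treatment also ends treatment, and SAP 6.1.1.2 counts it as clinical failure once three doses have been given. Restricting the analysis to completers removes these subjects although their outcome is known and would be carried forward as failure.

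The study has one arm, no comparator and no hypothesis test, so the reported rates are the efficacy evidence. A second, higher success rate beside the MITT rate, without a definition or label, could be taken as the success rate in adequately treated children, when part of the difference comes only from who was left out.

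**Working it through.** **No planned figure to reproduce.** Protocol 9.4 says no sample size calculation was made, and neither document gives an expected completion or discontinuation rate. The check therefore asks which way the rate moves, and over what range under stated assumptions.

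**Inputs**

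- N = 60, the planned number of dosed subjects with confirmed Candida infection (SAP 2.1.2; protocol 9.4).
- S = 45 successes (75.0%). Assumption: near the adult EOIVT success rate of 75.6% in protocol 1.3.2. S = 36 (60.0%) is a lower alternative.
- k = failures removed because they stopped early; m = successes removed because they stopped early. Both are assumed.
- Exact Clopper-Pearson 95% intervals, as in SAP 8.1.1.

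**Formulas.** MITT rate = S/N. Completer rate = (S − m)/(N − k − m).

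**Results for S = 45.** MITT: 45/60 = 75.0% (62.1 to 85.3).

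| k | m | Completer rate (95% CI) | Shift, points |
|---|---|---|---|
| 3 | 0 | 45/57 = 78.9% (66.1 to 88.6) | +3.9 |
| 6 | 0 | 45/54 = 83.3% (70.7 to 92.1) | +8.3 |
| 9 | 0 | 45/51 = 88.2% (76.1 to 95.6) | +13.2 |
| 12 | 0 | 45/48 = 93.8% (82.8 to 98.7) | +18.8 |
| 6 | 4 | 41/50 = 82.0% (68.6 to 91.4) | +7.0 |
| 3 | 6 | 39/51 = 76.5% (62.5 to 87.2) | +1.5 |
| 3 | 9 | 36/48 = 75.0% (60.4 to 86.4) | 0.0 |

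**Results for S = 36.** MITT is 36/60 = 60.0%. With m = 0 and k = 3, 6, 9, 12 the completer rate is 63.2%, 66.7%, 70.6% and 75.0%.

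**One age stratum of 20.** With 15/20 = 75.0%, removing 3 failures gives 15/17 = 88.2%.

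**Break-even at 75%.** Setting (45 − m)/(60 − k − m) = 0.75 gives 45 − m = 45 − 0.75k − 0.75m, so m = 3k. The upward shift disappears only if three of every four early stoppers were successes, and reverses only if more were. Persistent-candidemia subjects contribute only to k. In addition, under SAP 6.1.1.2 further antifungal treatment not documented as prophylactic counts as clinical failure, which makes it harder for an early stopper to be a success.

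**With declared failures kept in.** If only the m early-stopping successes are dropped, the rate is (45 − m)/(60 − m): 43/58 = 74.1%, 41/56 = 73.2% and 39/54 = 72.2% for m = 2, 4 and 6. This takes all 15 non-successes to be declared failures. Early stoppers with an indeterminate or missing outcome would still drop out.

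**The case against.** The strongest reply is that the analysis is minor and the selection only partial. Much of this stands.

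- The main global response analysis uses the whole MITT set with missing counted as failure. Efficacy endpoints are all secondary, safety is primary, and SAP 4.2 rules out hypothesis tests. SAP 8.2.4.1 and 8.2.4.4 tabulate discontinuations by age category, so a careful reader could see that subjects had been lost.
- Not every early stop is a failure. Protocol 6.9 says that subjects crossing its liver-test thresholds "must be discontinued from treatment with anidulafungin", and protocol 6.7 allows withdrawal at the subject's own request. Neither is tied to response. When many successes stop, the shift is small, as the +1.5 row shows.
- Keeping declared failures while dropping early-stopping successes selects in the other direction. That is a real cost of the fix.

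Two stronger readings are tempting. A reader might infer that the analysis strips out failures in general. It does not: subjects who finish treatment and are clinical failures, relapse, acquire a new infection, or are imputed to failure for other antifungal use (SAP 6.1.1.2, 6.1.3, 6.1.4) all stay in. A reader might also infer that the completer rate says nothing about efficacy. That goes too far: it describes outcome given completion, which is selective but not empty.

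The reply leaves one fact in place: as written, the analysis leaves out at least one class of subject whose failure is declared by protocol rule and whose outcome is known.

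**Conclusion.** The point holds in limited form. Persistent-candidemia failures, and Candida deaths on treatment, fall outside the completer set on any ordinary reading of completion, so the completer rate will tend to lie above the MITT rate. The size cannot be fixed from the documents. Under an assumed 75.0% MITT rate it runs from +1.5 points (3 failures and 6 successes stop) to +18.8 points (12 failures and no successes stop), with no shift at m = 3k. The upper end depends on no success stopping early and should not be taken as a forecast.

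The documents do not support the inference that the study's main efficacy result is inflated. The full-MITT analysis keeps these subjects as failures. What is at risk is the interpretation of one additional, undefined and unlabelled secondary figure.

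**What to change.** In SAP 8.2.2, either:

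- apply the SAP 5.3.1 exception, so that the analysis includes subjects who completed study treatment or who stopped after being declared a clinical and/or microbiologic failure, the latter counted as failures. This covers persistent candidemia and deaths that meet the SAP's clinical failure definition (due to Candida infection, after at least three doses), not every death; or
- replace the completers analysis with a Per-Protocol analysis. SAP section 5 already names that set as supportive, but no Per-Protocol analysis is scheduled in 8.2.2 or 8.2.5. The set also brings further exclusions, for example for prior antifungal therapy and retained devices.

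In either case, define completion of study treatment, add the analysis to the 8.2.5 table as supportive, and report the number excluded and the reasons beside the MITT rate.

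The cost is one clause, a definition and a table row; no new data are needed. The figure will be less favourable and, because successes who stop early are still dropped, may fall slightly below the MITT rate: 39/54 = 72.2% against 75.0% if 6 such successes are dropped.
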